6.5 Criteria for Removal from Study

Patients will be removed from study when any of the criteria listed in Section 6.3 applies. The reason for study removal and the date the patient was removed must be documented in the Case Report Form.

7. DOSING DELAYS/DOSE MODIFICATIONS/SAFETY CONSIDERATIONS

According to design of drug administration, patients not experiencing DLTs in the first week of the first cycle with 20 mg/m² (defined as any grade ≥ 3 non-hematologic toxicity (except grade ≥ 2 neurotoxicity), or grade ≥ 4 neutropenia or thrombocytopenia lasting ≥ 7 days) will undergo dose escalation from the second week to 56 mg/m². Before each drug dose, the patient will be evaluated for possible toxicities that may have occurred after the

previous dose(s). Toxicities are to be assessed according to the NCI Common Terminology Criteria for Adverse Events (CTCAE), Version 4.03 (Appendix D).

Carfilzomib is to be restarted at the same schedule the patient was on before therapy was held, and the dose must be reduced for toxicities as follows:

- If the patient was receiving 56 mg/m², reduce the dose to 45 mg/m².
- If the patient was receiving 45 mg/m², reduce the dose to 36 mg/m².
- If the patient was receiving 36 mg/m², reduce the dose to 20 mg/m².
- If the patient was receiving 20 mg/m², reduce the dose to 15 mg/m².

Dose reductions for Hematologic Toxicities

Study drug will be withheld from subjects with:

- Grade 4 lymphopenia persisting for > 14 days, if lymphopenia was not pre-existing
- Grade 4 thrombocytopenia with active bleeding
- Grade 4 anemia and thrombocytopenia requires the carfilzomib dose to be withheld. Subjects should receive supportive measures in accordance with institutional guidelines.

The following table outlines the dose reduction guidelines for carfilzomib for thrombocytopenia and neutropenia:

Thrombocytopenia	
	Recommended Action
When Platelets:	Carfilzomib
Fall to < 30 × 10 ⁹ /L	Interrupt carfilzomib, follow CBC weekly
Return to ≥ 30 × 10 ⁹ /L	Resume at full dose
Subsequently drop to < 30 × 10 ⁹ /L	Interrupt carfilzomib, follow CBC weekly
Return to ≥ 30 × 10 ⁹ /L	Resume at 1 dose decrement

Neutropenia	
	Recommended Action
When ANC	Carfilzomib
Falls to < 0.5 × 10 ⁹ /L	Interrupt carfilzomib add filgrastim per ASCO guidelines if Gr ≥3 with fever, follow CBC weekly
Returns to > 1.0 × 10 ⁹ /L (if neutropenia was the only toxicity noted)	Resume at full dose

Returns to $> 1.0 \times 10^9/L$ (if other toxicity noted)	Resume at 1 dose decrement
Subsequently drops to $< 0.5 \times 10^9/L$	Interrupt carfilzomib
Returns to $> 1.0 \times 10^9/L$	Resume at 1 dose decrement

Dose Reductions for Non-Hematologic Toxicities

Study drug should be held for \geq Grade 3 events until resolved to \leq Grade 1 or return to baseline. After resolution of the event to \leq Grade 1 or return to baseline, if the adverse event was not treatment-related, subsequent treatment with carfilzomib may resume at full dose. If the event was treatment-related, subsequent treatment with carfilzomib will resume at one level dose reduction. If toxicity continues or recurs, further carfilzomib dose reduction may be permitted at the discretion of the investigator. If toxicity continues to recur after dose reduction to 15 mg/m², the subject should be removed from study. If there is no resolution of toxicity after 3 weeks of withholding treatment, the subject will be withdrawn from the study.

Dose adjustment guidelines for non-hematologic toxicities are summarized as follows:

Symptom	Recommended Action
	Carfilzomib
Allergic reaction/hypersensitivity	
Grade 2 – 3	Hold until \leq Grade 1, reinstitute at full dose.
Grade 4	Discontinue
Tumor lysis syndrome (≥ 3 of following: $\geq 50\%$ increase in creatinine, uric acid, or phosphate; $\geq 30\%$ increase in potassium; $\geq 20\%$ decrease in calcium; or ≥ 2 -fold increase in LDH)	Hold carfilzomib until all abnormalities in serum chemistries have resolved. Reinstitute at full doses.
Infection Grade 3 or 4	Hold carfilzomib until systemic treatment for infection complete. If no neutropenia, restart at full dose. If neutropenic, follow neutropenic instructions.
Herpes zoster or simplex of any grade	Hold carfilzomib until lesions are dry. Reinstitute at full dose
Gr 2 treatment emergent neuropathy with pain	Continue to dose. If neuropathy persists for more than two weeks hold carfilzomib until resolved to \leq Gr 2 without pain. Then restart at 1 dose decrement

Grade \geq 3 neuropathy	Discontinue
Renal Dysfunction	
CrCl <30 mL/min	Hold until CrCl \geq 30 mL/minute; restart at 1 dose decrement
Congestive heart failure	Any subject with symptoms of congestive heart failure, whether or not drug related, must have the dose held until resolution or return to baseline, after which treatment may continue at a reduced dose, or the subject may be withdrawn from the study. If no resolution after 2 weeks, the subject will be withdrawn from the study.
Other non-hematologic toxicity assessed as carfilzomib-related \geq Grade 3	Hold dose until toxicity resolves to \leq Grade 1 or baseline. Restart at 1 dose decrement.

Increased Creatinine or Decreased CrCl

Study drug should be held for CrCl < 30 mL/min. A phase I study of Carfilzomib in patients with relapsed and refractory multiple myeloma and varying degrees of renal insufficiency was reported at the 2009 American Society of Hematology meeting. At the time of this preliminary analysis, 22 patients had been treated on the trial. Ten patients had creatinine clearance \geq 80 mL/min; 9 had creatinine clearance 50-79 mL/min; 9 patients had creatinine clearance 30-49 mL/min; 9 patients had creatinine clearance < 30 mL/min and 2 patients were on chronic dialysis. Adverse events in these patient groups were similar regardless of degree of renal dysfunction and included anemia, fatigue, and diarrhea as the most common adverse events observed.

Renal Dysfunction	Recommended Action
Normal to mild (CrCl \geq 30 mL/min)	Full dose
Severe (CrCl \leq 30 mL/min)	Severe CrCl < 30 mL/min/Hold carfilzomib until CrCl \geq 30 mL/min; restart at one level dose reduction

Infections

Subjects with active or suspected infections should have treatment withheld until infection has resolved and anti-infective treatment has been completed. After the infection has resolved and anti-infective treatment has been completed, treatment may continue at the original dose. If there is no resolution of toxicity after 3 weeks, the subject will be withdrawn from the study.

Congestive Heart Failure (CHF)

Any subject with symptoms of CHF or any other suspected acute cardiac event, whether or not drug related, must have the dose held until resolution. After the event has resolved or returned to baseline, treatment may continue at a reduced dose, with the approval of the Onyx Medical Monitor, or the subject may be withdrawn from the study. If there is no resolution of CHF after 2 weeks, the subject will be withdrawn from the study.

Conditions Not Requiring Dose Reduction

The following conditions are exceptions to the above guidelines. Carfilzomib does not need to be held in the following cases:

- Grade 3 nausea, vomiting or diarrhea (unless persisting > 3 days with adequate treatment of anti-emetics or anti-diarrheals)
- Grade 3 fatigue (unless persisting for >14 days)
- Alopecia
- \geq Grade 3 hyperglycemia attributed to dexamethasone

Missed Doses

Missed doses will not be replaced during a cycle. If a subject misses more than 2 doses of any cycle for reasons other than toxicity, the subject will be discontinued.

Changes in Body Surface Area (BSA)

Dose adjustments do not need to be made for weight gains/losses of $\leq 20\%$. Subjects with a Body Surface Area (BSA) $> 2.2 \text{ m}^2$ will receive a capped dose of 44 mg of carfilzomib (at the 20 mg/m^2 dose level) or 123 mg of carfilzomib (at the 56 mg/m^2 dose level).

Safety Considerations

Based upon the experience in the Phase 1 and 2 clinical studies with carfilzomib, the following observations are noted:

- A “first dose effect” has been seen, which is notable for fever, chills, rigors, and/or dyspnea occurring during the evening following the first day of infusion and an increase in creatinine on Day 2, which may be the clinical sequelae of rapid tumor lysis and/or cytokine release.
- Should a “first dose” effect occur at any point during Cycle 1 or 2, treatment with high dose glucocorticoids (e.g. methylprednisolone 50–100 mg) is recommended. In addition, intravenous fluids, vasopressors, oxygen, bronchodilators, and acetaminophen should be available for immediate use and instituted, as medically indicated.
- Dexamethasone 4 mg PO/IV will be administered prior to all carfilzomib doses during the 1st cycle and prior to all carfilzomib doses during the first dose-escalation (56 mg/m^2) cycle. If treatment-related fever, rigors, chills, and/or dyspnea are observed post any dose of carfilzomib after dexamethasone has been discontinued, dexamethasone (4 mg PO/IV) should be re-started and administered prior to subsequent doses.
- Acyclovir or similar should be given to all subjects unless contraindicated.

- CrCl changes are mostly transient, reversible, and non-cumulative. All subjects should be well hydrated. Clinically significant electrolyte abnormalities should be corrected prior to dosing with carfilzomib. Renal function must be monitored closely during treatment with carfilzomib. Serum chemistry values, including creatinine, must be obtained and reviewed prior to each dose of carfilzomib during Cycles 1 and 2. Carfilzomib must be held for subjects with a CrCl < 15 mL/min at any time during study participation as outlined.
- Subjects with active or suspected infection of any kind that required systemic treatment should not be dosed with carfilzomib until the infection has resolved and if being treated with anti-infective, the course of antibiotics has been completed.
- Thrombocytopenia has been transient and typically resolves during the week between treatments. For platelet counts $\leq 25,000/\text{mm}^3$, carfilzomib dosing must be held. If platelet counts do not recover, the dose of carfilzomib may be reduced or held according to the Dose Reductions / Adjustments rules outlined in this protocol.
- Subjects should have anemia corrected in accordance with the Institutional guidelines.
- Carfilzomib treatment can cause nausea, vomiting, diarrhea, or constipation sometimes requiring the use of anti-emetics or anti-diarrheals. Fluid and electrolyte replacement should be administered to prevent dehydration.

Concomitant Medications

Concomitant medication is defined as any prescription or over-the-counter preparation including vitamins and supplements. Concomitant medications should be recorded from 14 days before Day 1 through the end of the subject's study participation. Any change in concomitant medications must be recorded.

Required Concomitant Medications

Female subjects of child-bearing potential must agree to use dual methods of contraception for the duration of the study. Male subjects must agree to use a barrier method of contraception for the duration of the study if sexually active with a female of child-bearing potential. Dexamethasone 4 mg PO/IV will be administered prior to all carfilzomib doses during the first cycle and prior to all carfilzomib doses during the first dose-escalation cycle. If treatment-related fever, rigors, chills, and/or dyspnea are observed post any dose of carfilzomib after dexamethasone has been discontinued, dexamethasone (4 mg PO/IV) should be re-started and administered prior to subsequent doses. Subjects should receive acyclovir or similar (famciclovir, valacyclovir) anti-varicella (anti-herpes) agent prophylaxis.

Optional and Allowed Concomitant Medications

Allopurinol (in subjects at risk for tumor lysis) is optional and will be prescribed at the Investigator's discretion. These subjects may receive allopurinol 300 mg PO BID (Cycle 1 Day -2, Day -1), continuing for 2 days after Cycle 1 Day 1 (total of 4 days), then reduce dose to 300 mg PO QD, continuing through Day 17 of Cycles.

Subjects may receive RBC or platelet transfusions if clinically indicated in accordance with institutional guidelines. Subjects who require repeated platelet transfusion support

should be discussed with the Lead Principal Investigator. Approved bisphosphonates and erythropoietic agents are allowed. Subjects may receive anti-emetics and anti-diarrheals as necessary, but these should not be administered unless indicated. Colony-stimulating factors may be used in accordance with ASCO guidelines if neutropenia occurs but should not be given prophylactically. Antibiotic prophylaxis with ciprofloxacin or other fluoroquinolone (or trimethoprim/ sulfamethoxazole if fluoroquinolones are contraindicated) is per physician discretion.

Subjects may receive RBC or platelet transfusions, if clinically indicated, per institutional guidelines. Subjects who require repeated platelet transfusion support should be discussed. Subjects may receive supportive care with erythropoietin or darbepoetin, in accordance with institutional guidelines. Vitamins and supplements should be recorded on the concomitant medication page. All transfusions and/or blood product related procedures must be recorded on the appropriate form.

Excluded Concomitant Medications

Concurrent therapy with an approved or investigative anticancer therapeutic with activity against multiple myeloma is not allowed. Other investigative agents (e.g., antibiotics or anti-emetics) should not be used during the study.

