3. OVERALL TRIAL DESIGN

3.1 Design

This is a 2-center one-stage phase II trial conducted at UAB Comprehensive Cancer Center and outside sites, and managed by the CTNMO (Clinical Trial Network Monitoring Office) housed at the UAB Comprehensive Cancer Center. Clinical PFS as the primary end-point and the trial will enroll 28 patients. The eligible population includes men with metastatic CRPC who have received prior abiraterone and/or enzalutamide (prior chemotherapy and sipuleucel-T are allowed). Carfilzomib is administered twice-weekly on consecutive days (± 1 day) (days 1, 2, 8, 9, 15, 16) as a 30 minute intravenous (IV) infusion for 3 weeks every 4 weeks (1 cycle) with dexamethasone and acetaminophen premedication as well as normal saline 250 ml over 30 mins as pre-hydration. The dose of carfilzomib is 20 mg/m² on days 1 and 2 of cycle 1 and then escalated in succeeding weeks and cycles to 56 mg/m² for no dose limiting toxicities (DLTs) occur. DLTs are defined as any grade ≥ 3 non-hematologic toxicity or grade ≥ 4 neutropenia or thrombocytopenia lasting ≥ 7 days. Acyclovir 400 mg orally twice daily is required during therapy, which may be discontinued ≥ 7 days after the last dose of carfilzomib. Therapy will continue until progression (as defined below) or severe toxicities. Patients removed from the trial for toxicities or other reasons will continue to be followed until progression or starting a new agent. Androgen deprivation therapy with LHRH analogue or antagonist and bone protecting agent (denosumab or zoledronic acid) will also continue. Comprehensive metabolic panel (CMP) evaluations are performed on day 1 every 4 weeks, complete blood cell (CBC) counts on days 1, 8 and 15 every cycle, and radiological evaluations are performed every 3 cycles or earlier if clinically indicated. Pain (PPI score, Appendix B) and analgesic intake (Appendix C) are recorded on day 1 of every cycle. Correlative studies include serial CTC enumeration (repeated on day 1 cycle 2, then q 3 cycles) and collection of whole blood is performed at baseline for 20S proteasome activity. Progression of disease will be defined clinically as the first occurrence of any of the following, and PSA progression alone will not constitute progression:

1. Two distinct new lesions on bone scan consistent with bone metastases in the best judgment of the investigator and confirmed by further new lesions on a subsequent scan ≥ 6 weeks later.

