8. STUDY CALENDAR

Baseline evaluations are to be conducted within 2 weeks prior to administration of protocol therapy. Scans and x-rays must be done ≤4 weeks prior to the start of therapy. In the event that the patient's condition is deteriorating, laboratory evaluations should be repeated within 48 hours prior to initiation of the next cycle of therapy.

	-28 days	-14 days (may serve as cycle 1 day 1 labs)	Day 1 (± 1 day) of every cycle (28 days)	Day 8 and 15 every cycle (± 1 day)	Day 1 Every 3 cycles	30 (± 7 days) post last treatment
ASSESSMENTS						
History and exam (H&P)	X		X			X ¹
ECOG performance status		X	X			X ¹
CBC with differential		X	X	X		X ¹
CMP		X	X			X ¹
PSA		X	X			X ¹
LDH		X				
Testosterone level		X				
Pain (PPI 0-5 scale)		X	X			X ¹
Analgesic intake (increased, decreased or stable)		X	X			X ¹
Echocardiogram	X		X ^{6,7}			
DISEASE ASSESSMENT						

CT chest , abdomen, pelvis	X				X	X ¹
Bone Scan	X				X	X ¹
TREATMENT						
Carfilzomib day 1,2, 8,9,15,16 (30 min IV infusion)			X ²	X ²		
Premedication (Dexamethasone, Acetaminophen)			X ³	X ³		
Pre-hydration (Normal saline 250-500 ml over 30 minutes)			X ⁴	X ⁴		
Acyclovir 400 mg PO bid			X ⁵	X ⁵		
LHRH analogue (if no prior orchiectomy)					X	
CORRELATIVE STUDIES						
CTC enumeration (3 time points)	X		X (cycle 2 only)		X (cycle 4 only)	
Whole Blood 20S proteasome assay	X					
FOLLOW-UP						
Disease progression and survival						X ¹

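### Grade 4 platelets on day 8 (and, on one reading, neutrophils) cannot yet be classed as a DLT, and the restart dose after the hold reads as 20 or 56 mg/m²

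*Combined protocol and SAP*

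**What the plan says.** Section 7 sets the escalation rule. It applies to "patients not experiencing DLTs in the first week of the first cycle with 20 mg/m²", and its hematologic part is "or grade ≥ 4 neutropenia or thrombocytopenia lasting ≥ 7 days) will undergo dose escalation from the second week to 56 mg/m²". The Synopsis, Sections 3.1 and 6.1 and Study Calendar footnote 2 also make escalation to 56 mg/m² depend on having no DLT, but none of them limits this to the first week.

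Section 3.1 schedules "complete blood cell (CBC) counts on days 1, 8 and 15 every cycle". The Study Calendar gives these visits a ±1 day window and says that a sample from the 14 days before treatment "may serve as cycle 1 day 1 labs".

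For low counts, the Section 7 tables tell the site to stop when platelets fall below 30 × 10⁹/L ("Interrupt carfilzomib, follow CBC weekly") or ANC falls below 0.5 × 10⁹/L. After a first fall and recovery (platelets at least 30; ANC above 1.0, with no other toxicity) the instruction is "Resume at full dose". A second fall, or neutropenia accompanied by another toxicity, leads to a one-level decrement. Above the tables, a general sentence on restarting says "the dose must be reduced for toxicities as follows", and the last step of the list is "If the patient was receiving 20 mg/m², reduce the dose to 15 mg/m²". *Full dose* is not defined.

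**The concern.** The decision and the evidence for it fall at different times. The escalation decision is taken on day 8. The hematologic DLT needs 7 days of grade 4 counts, and on day 8 there is only one count after treatment started. A brief drop and a persistent one look the same that day.

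The hold rules protect the patient on day 8 but do not say what he receives next. The tables were written for a patient already at a settled dose. A patient held between the 20 mg/m² lead-in and the 56 mg/m² target has two candidates for *full dose*. Footnote 2 adds a separate route to 56 mg/m², because an episode not shown to last 7 days is not a DLT.

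At stake is a safety instruction. Section 1.3 names thrombocytopenia and neutropenia as the dose-limiting toxicities of single-agent carfilzomib. As written, the protocol lets a site go to 56 mg/m² directly after a grade 4 drop on two 20 mg/m² doses, with platelets recovered only to 30 × 10⁹/L. Another site could restart a similar patient at 20 mg/m².

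**Working it through.** The plan gives no figure for this point, so the check sets the schedule against the rule and then traces the restart dose.

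**Inputs**
- Dosing on days 1, 2, 8, 9, 15 and 16; 20 mg/m² on days 1 and 2, then 56 mg/m² (Section 6.1).
- Blood counts on days 1, 8 and 15, ±1 day (Section 3.1, Study Calendar).
- Day 1 is a baseline value, and Section 4.2 excludes platelets below 100,000/mm³ and ANC below 1500/mm³.
- No other week-1 blood count is required. The extra pre-dose tests in cycles 1 and 2 are serum chemistry (Section 7, Safety Considerations), and the toxicity check before each dose names no blood count.
- Missed doses are not made up within a cycle (Section 7, Missed Doses).

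**Step 1: what is known on day 8**
- First dose to day-8 count: 8 − 1 = 7 days; second dose to that count: 8 − 2 = 6 days. With ±1 day on both visits, the first interval runs from 7 − 2 = 5 to 9 − 0 = 9 days.
- Counts after the first dose: one. Documented grade 4 duration: 8 − 8 = 0 days, against 7 required. On the nominal schedule, a true 7-day episode by day 8 would need onset at the first infusion.

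**Step 2: what is known on day 15**
- Grade 4 on both counts: 15 − 8 = 7 days documented on the nominal schedule, or 14 − 9 = 5 to 16 − 7 = 9 with the windows. The earliest possible recognition is day 7 + 7 = day 14. By then the Section 7 first-week window has closed, while the texts without a week limit would still count the event.
- Recovered by day 15: onset lay between days 1 and 8 and recovery between days 8 and 15, so the true duration is above 0 and below 15 − 1 = 14 days. Whether a DLT occurred cannot be determined.

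**Step 3: restart dose in a worked case**

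Take a first, isolated grade 4 platelet count on day 8, recovered on day 15.
- *20 mg/m²*: the table's *full dose* means the dose before the hold. The Section 7 text on infections supports this by analogy: its table says *full dose* where the paragraph on infections says *original dose*. Nothing says so for cytopenias.
- *56 mg/m²*: *full dose* means the target, or footnote 2 applies because no DLT was shown.
- Ratio: 56 / 20 = 2.8.

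**Step 4: cycle-1 total** (days 8 and 9 withheld and not replaced)
- Restart at 20: 2 × 20 + 2 × 20 = 80 mg/m².
- Restart at 56: 2 × 20 + 2 × 56 = 152 mg/m².
- Patient with no hold: 2 × 20 + 4 × 56 = 264 mg/m².

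**Primary design**

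The 6-of-25 rule gives exact type I error 0.0334 at a 10% rate and power 0.8065 at 30%, in line with the stated 0.05 and 80%. Dose enters neither calculation.

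**The case against.** The strongest reply is that the rules work together. The hold stops dosing on day 8, weekly counts follow, and a drop that persists can be identified about day 15 before any further drug is given. This stands. A reader might infer that the hematologic criterion never operates, or that patients receive 56 mg/m² while grade 4. The documents support neither: the criterion resolves about a week late, and the drug is withheld meanwhile.

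A reader might also infer a third restart dose, 15 mg/m², from the general sentence that doses must be reduced and the 20-to-15 step. That does not hold for a first isolated cytopenia. The table specific to that event says to resume at full dose; the list gives the size of a decrement where one is due. For these cytopenias, 15 mg/m² applies only where the table calls for a decrement, such as neutropenia with another toxicity or a second fall.

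The 7-day duration may attach grammatically to thrombocytopenia alone. A grade 4 neutrophil count on day 8 would then be a DLT at once and would block escalation as intended. The wording does not settle this, so the timing problem is certain only for platelets.

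Section 14 makes the principal investigator the contact for dose modifications and has each patient discussed weekly. That makes unnoticed divergence between sites less likely, but it does not define the dose. Finally, ignoring brief drops is a legitimate choice, and Section 7 describes thrombocytopenia as transient. The 7-day definition itself need not change.

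**Conclusion.** The point holds and is minor. At the day-8 decision a thrombocytopenia DLT cannot be recognised on the scheduled counts; nor can a neutropenia DLT if the duration covers both. Recognition comes about day 15, outside the first-week window in Section 7 but inside the unrestricted wording elsewhere. The consequence is an undefined restart dose of 20 or 56 mg/m², a 2.8-fold difference, or 80 against 152 mg/m² over cycle 1 in the worked case.

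This assumes that only the scheduled counts are taken and that grade 4 counts fall below the hold thresholds; the protocol links to CTCAE 4.03 without printing the cut-offs.

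The number of patients affected is unknown and probably small. The documents give no week-1 grade 4 rate. The nearest figure is in Section 1.3: among 47 solid tumor or lymphoma patients, the two most common related grade 3 or higher events were anemia (5) and fatigue (4). Related thrombocytopenia and neutropenia of that grade were therefore each at most 4/47 = 8.5%, over all treatment and at doses up to 20/70 mg/m². That is an indication only, not a bound for week 1 of this trial.

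A reader might infer a threat to the primary result. There is none in the test: type I error, power, the 28 patients and the 6-of-25 rule do not depend on this.

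**What to change.** - State that a patient held on day 8 under the platelet (<30 × 10⁹/L) or ANC (<0.5 × 10⁹/L) rule does not escalate in cycle 1. Using the hold thresholds rather than grade 4 covers every patient who is held.
- Define *full dose* as the dose level before the hold, here 20 mg/m². The step to 15 mg/m² applies only where the tables call for one decrement.
- State that this patient escalates to 56 mg/m² from cycle 2 day 1 if that day's count meets the existing recovery thresholds (platelets at least 30, ANC above 1.0) and no DLT has been documented.
- State that a grade 4 neutropenia or thrombocytopenia documented as lasting 7 days or more is a DLT whichever week it is documented in, and bars escalation.
- Use the same wording in the Synopsis, Sections 3.1, 6.1 and 7, and Study Calendar footnote 2.

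The edit is to protocol text only and uses counts already scheduled, with no added visits or data. The cost is that the few affected patients reach 56 mg/m² later. In the worked case a patient who would have restarted at 56 mg/m² receives 152 − 80 = 72 mg/m² less in cycle 1.
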